## 1.7. Benefit-Risk Assessment

SYNB1934 and its closely related strain SYNB1618 have been studied in more than 230 HVs and PKU participants. The safety profile has been consistent with the probiotic chassis EcN, which has been used in participants for decades in the European Union and Canada without requirement for prescription. There have been no treatment-related SAEs, no deaths, no systemic toxicity, and no infections. Interindividual variability in tolerability has been observed. The majority of TEAEs have been either mild or moderate in severity and reversible. Most AEs have been GI-related and included GI discomfort, nausea, and vomiting. At increasing doses, GI-related AEs, mainly nausea and vomiting, have been dose limiting. A small dose-related and reversible increase in CRP has been observed in some participants; the clinical significance of this finding is unclear. The CRP level has returned to normal after end of dosing.

Consistent with the design of SYNB1934, clearance is rapid following discontinuation of dosing. In study SYNB1618-CP-001, SYNB1618 was cleared within 4 days following the last dose, as indicated by fecal quantitative polymerase chain reaction (qPCR) analyses. Data from study SYNB1618-CP-002 are consistent. Across all study parts, following up to 7 days of repeat dosing with SYNB1618, no fecal sample was above the limit of quantification at 7 days after last dose. In neither study was there any evidence of colonization, nor did any participant require antibiotic treatment to achieve clearance. Clearance data for SYNB1934 are consistent with that for SYNB1618 with no subject having a positive qPCR sample more than 1 week after the last dose.

Data from completed studies demonstrates that SYNB1934 can access Phe from within the GI tract, as demonstrated by the D5-Phe meal challenge. A dose-related decrease in plasma D5-Phe AUC has been observed, with corresponding increase in strain-specific biomarkers plasma D5-TCA and urinary D5-HA. In the Phase 2 study SYNB1618-CP-003, SYNB1934 led to a mean 34% decrease in plasma Phe in PKU participants, thus demonstrating potential for clinical benefit in the treatment of PKU. Individual variability in Phe lowering was observed. Data from HVs in SYNB1934-CP-001 demonstrate increased Phe conversion capacity of SYNB1934 compared to SYNB1618 based on strain-specific biomarkers.

The risk of unintended effects of using genetically engineered EcN is considered low. The products of the 2 engineered Phe degradation pathways are TCA, produced via the PAL pathway, and PP, produced by the deamination of Phe by LAAD. TCA is a naturally occurring compound and is found in several plants that are consumed as food. It is frequently added to food

In the DEP, all enrolled participants will maintain a stable diet reflecting their baseline Phe intake and receive escalating doses of SYNBI934v1 from approximately 3 to 15 weeks to determine an iTD, which is defined as the highest dose the participant is able to tolerate. A participant will be defined as having reached an iTD if they tolerate 3 weeks at a dose, regardless of whether other doses are tolerated.

Blood Phe level will be measured at each dose level after 3 weeks at that level. A responder will be defined as a participant who achieves a  $\geq 20\%$  reduction in blood Phe level compared to DEP baseline on SYNBI934v1.

[figure not shown]
The DEP will contain an optional substudy (DEP weekly substudy) [REDACTED]

[REDACTED] Additional values obtained as part of the substudy will not be used to determine responder status.

Participants who complete at least 3 weeks at their iTD during the DEP will enter a 4-week RWP. Participants will be randomized 1:1 to receive SYNBI934v1 at their iTD determined in the DEP or placebo TID. Randomization will be stratified on screening Phe level. Blood Phe level will be measured at Weeks 1, 3, and 4 of the RWP. Participants will remain on the same diet they consumed during the DEP.

Participants who complete the 4-week RWP may enter the OLE and receive SYNBI934v1 for up to 36 months at their iTD. (At the sponsor's discretion, enrollment of new participants directly into OLE may be opened.) The iTD in Parts 1 and 3 can differ. Participants will be allowed to modify their standard diet if their blood Phe level is  $< 240 \mu\text{mol/L}$ , as determined by either local or central laboratory testing, with guidance from the investigator as outlined in the study-specific Diet Manual. The 3-day dietary intake assessments will be conducted per the Schedule of Events (Table 5).

**Figure 2: Study SYNBI934-CP-003 Schematic**

iTD = individually titrated dose. Should the DMC remove doses from the study after completion of the interim analysis, the dose ramp will be altered to reflect these changes.

### 3.2. Dosing and Dose Escalation

SYNBI934v1 will be taken with a meal throughout the study. Participants will take a proton pump inhibitor (PPI) once per day (QD), recommended to occur before breakfast, during all parts of the study (see Section 4.3.4), starting at Day -7 of the DEP. If participants are unable to tolerate the PPI, they may attempt to use an H2 blocker per investigator discretion. If neither the PPI nor H2 blocker can be tolerated, the participant will discontinue from the study.

- Decrease the frequency of dosing for 1 to 2 days. This can be initiated without the approval of the medical monitor.
- Skip dosing 1 to 2 days. This can be initiated without the approval of the medical monitor.
- Skip dosing  $\geq 3$  days. This must be discussed with the medical monitor.
- De-escalate to a previous level after discussion with the medical monitor. In this case, the participant will restart 3 weeks at a previously tolerated dose including its ramp, and this previously tolerated dose will be the iTD. After de-escalation, participants cannot escalate to a higher dose again during Part 1.

In general, a dose is considered intolerable if the participant experiences Grade 3 or more severe TEAEs or Grade 2 GI AEs that do not improve with continued dosing at the same dose level over time. If a dose is de-escalated due to a reason other than Grade 3 or greater or Grade 2 GI TEAEs, or a second de-escalation is required, the medical monitor must be consulted. Participants must take at least 8 of the 9 expected doses on the final 3 days of their iTD period. If not, the medical monitor must be consulted before the participant enters Part 2.

### **3.2.2. Part 2: Randomized Withdrawal**

In the RWP, participants who completed DEP will be randomized 1:1 to receive either SYNBI934v1 at their iTD established in the DEP or placebo. Participants will remain on this dose of investigational medicinal product (IMP; i.e., SYNBI934v1 or placebo) for the duration of the RWP, unless they develop intolerance or meet other discontinuation criteria (see Section 3.5). Doses of SYNBI934v1 cannot be modified during the RWP.

### **3.2.3. Part 3: Open-Label Extension**

During the OLE, all participants will complete a dose ramp to their iTD over time guided by tolerability, as described for the DEP, including the full dose ramp schedule (Table 4). The iTD in OLE may be different from the iTD in DEP or RWP. The investigator may escalate the dose of SYNBI934v1 up to a maximum of  $1 \times 10^{12}$  live cells based on tolerability; multiple attempts to escalate to a higher dose level are permitted per investigator discretion.

## **3.3. Diet and Phenylalanine Monitoring**

For 3 consecutive days prior to scheduled study visits and blood Phe draws, all participants will have a 3-day dietary intake assessment (see Table 5). A study dietitian will interview the participant and provide advice on maintaining a diet that is consistent with baseline diet throughout the study. Participants will follow their usual diet (including Phe, protein, and medical food intake) from baseline in the DEP to the end of the RWP.

During the DEP and RWP, blood Phe levels will be blinded to the sponsor, participant and investigator. The investigator will be notified by the central laboratory if Phe is  $> 1.5 \times$  the DEP baseline value, if Phe falls below  $30 \mu\text{mol/L}$  or if Tyr falls below  $20 \mu\text{mol/L}$ , based on a defined monitoring plan (to be provided in the Study Manual; see also Section 8.11). During the OLE, participants will be allowed to modify their standard diet if their blood Phe level is  $< 240 \mu\text{mol/L}$ , as determined by either local or central lab, with guidance from the investigator as

outlined in the study-specific Diet Manual. The 3-day dietary intake assessments will continue per the Schedule of Events (Table 6).

### 3.4. Study Stopping Rules

If any of the following criteria are met, enrollment will be halted. Participants already enrolled in the study will continue dosing until review by the Data Monitoring Committee (DMC).

1. Two or more participants experience an AE  $\geq$  Grade 3, per protocol severity grading criteria, related to SYN1934v1 as assessed by the investigator.
2. Clinical infection is detected in a sterile space with a gram-negative aerobic bacillus confirmed by qPCR to be SYN1934v1.

If any of the above criteria are met, the DMC will review all relevant data and determine whether enrollment in the study should resume and whether any modifications to the study are warranted. If the DMC decides that further enrollment should be permanently suspended, subjects already enrolled in the study will continue to be followed for the duration of the study.

If a death occurs at any time during the study that is considered by the investigator to be related to SYN1934v1, enrollment will be halted and dosing for subjects already enrolled will be stopped until the DMC reviews all relevant data and makes further recommendations.

This study may also be discontinued at any time due to safety concerns (including, but not limited to, the stopping rules described below), failure to meet expected enrollment goals, administrative reasons, or at the discretion of the sponsor. Should the study be terminated prematurely, the sponsor will provide written notification to the investigator and regulatory authorities and will specify the reasons for early termination. The investigator must inform the Institutional Review Board (IRB), Independent Ethics Committee (IEC), or Research Ethics Board (REB) promptly and provide the reasons for the termination.

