### 6.3. Adverse Events of Special Interest

An adverse event of special interest (AESI), whether serious or nonserious, is one of scientific and medical concern specific to SYN1934v1 for which ongoing monitoring and rapid communication by the investigator may be appropriate. Based on current preclinical and clinical data, the following AEs will be considered AESIs and should be reported to the Sponsor within 24 hours of awareness.

Adverse events of special interest for SYN1934v1 are as follows:

- Hypersensitivity reactions due to SYN1934v1.
- Infections due to SYN1934v1.
- Grade  $\geq 3$  gastrointestinal AEs per protocol specified grading criteria, including nausea, vomiting, diarrhea, and abdominal pain.

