### 6.4. Reporting of Adverse Events

All AEs, serious and nonserious, will be fully documented on the appropriate eCRF. For each AE, the investigator must provide its duration (start and end dates or ongoing), intensity, assessment of causality, and whether specific action or therapy was required.

All AEs occurring from the time a participant signs the ICF through the safety follow-up period and at least one month following the last dose of SYN1934v1 must be recorded on the eCRF.

All AESIs and SAEs, regardless of relationship to SYN1934v1 or ██████████, must be reported to the Sponsor/designee on the applicable eCRF form within 24 hours of awareness. In addition, AESI or SAE forms should be uploaded and submitted to [[contact]](mailto:[contact]) within 24 hours of awareness. All AESIs and SAEs, regardless of relationship to study drug, will be followed by the Investigator until satisfactory resolution or the Investigator deems the SAE to be chronic or stable. After the final follow-up visit, only IMP-related AEs/SAEs need to be collected and reported.

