## **10. DATA RECORDING, RETENTION, AND MONITORING**

### **10.1. Case Report Forms**

Data will be collected using source documents through an electronic data capture system at the clinical site. The investigator or designee will record data specified in the protocol using eCRFs. Changes or corrections to eCRFs will be made by the investigator or an authorized member of the study staff according to the eCRF completion guidelines. It is expected that the site will enter all data within 5 business days of a participant visit.

It is the investigator's responsibility to ensure eCRFs are complete and accurate, regardless of whether this responsibility has been delegated in whole or in part. Following review and approval, the investigator or designee will electronically sign and date the pages, which certifies that the investigator has thoroughly reviewed and confirmed all data on the eCRF.

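### Related Grade 3 or higher AEs that are neither SAEs nor AESIs count toward the enrolment halt but have no expedited reporting route, so the halt can be delayed

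*Protocol*

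**What the plan says.** Protocol 3.4 opens its stopping rules with "If any of the following criteria are met, enrollment will be halted". Criterion 1 begins "Two or more participants experience an AE" of Grade 3 or higher, and continues "per protocol severity grading criteria, related to SYN1934v1 as assessed by the investigator". It has no restriction to serious events, to GI events or to one site. Once a criterion is met, the DMC reviews the data and decides whether enrolment resumes.

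Section 6.4 sets the expedited duty. AESIs and SAEs "must be reported to the Sponsor/designee on the applicable eCRF form within 24 hours of awareness". Section 6.3 names three kinds of AESI: "Hypersensitivity reactions due to SYN1934v1"; "Infections due to SYN1934v1"; and, at Grade 3 or higher, "gastrointestinal AEs per protocol specified grading criteria, including nausea, vomiting, diarrhea, and abdominal pain".

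Every other AE follows the routine data route in 10.1: "It is expected that the site will enter all data within 5 business days of a participant visit". Section 6.7 gives the DMC, the investigator and the sponsor's medical monitor a continuing duty to review safety data, and leaves the details to the DMC charter, which is not among the documents.

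**The concern.** The halt rule and the rapid-reporting rule use different lists of events, and the halt list is the wider one. Criterion 1 is a count over the whole study, so an investigator with one case cannot tell that another site has the second. Only someone who receives reports from all sites can see that the rule has been met, and for part of the counted events the protocol does not require those reports to arrive quickly.

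What is at stake is timing. Two related severe events could occur at two sites while enrolment continues, including any direct enrolment into the OLE that the sponsor may open under 3.1. The DMC review that the rule is meant to start would begin late as well.

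**Working it through.** The documents give no operating characteristic for the halt rule, so there is no stated figure to reproduce. The check sets the two scopes side by side and then adds up the stated intervals.

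**Scope**

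| Event | Counts toward a halt (3.4)? | 24-hour report (6.3, 6.4)? |
|---|---|---|
| Related SAE, Grade 3 or higher | Yes, criterion 1 | Yes |
| Related GI AE, Grade 3 or higher | Yes, criterion 1 | Yes, AESI |
| Hypersensitivity due to product, Grade 3 or higher | Yes, criterion 1 | Yes, AESI at any grade |
| Sterile-space infection confirmed as the product | Yes, criterion 2 | Yes, AESI at any grade |
| Related death | Yes, separate rule | Yes, SAE |
| Related AE, Grade 3 or higher, neither SAE nor AESI | Yes, criterion 1 | **No** |

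The last row is not empty by definition. Section 6.1.1 includes medically significant events in Grade 3, and these need not be serious. Section 6.2.1 says that even Grade 4 events, with thrombocytopenia as its example, are not always serious. It also keeps emergency room visits and short observation stays out of SAE reporting.

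**Timing inputs**
- Listed events: 24 hours from awareness, 1 day (6.4).
- Routine entry: 5 business days after a visit (10.1), taken as 7 calendar days.
- DEP: blood-draw visits 3 weeks apart, 21 days, with a 3-day window (Table 5).
- RWP: longest gap is Week 1 to Week 3, 14 days, with the same window.
- Weekly site contact in the DEP and RWP: 7 days (Table 5).
- OLE: visits every 90 days, plus or minus 5 (Table 6).

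**Lag to eCRF entry for an event in the last row**
1. The site learns of it at a visit: 7 days, against 1 day for a listed event.
2. The event starts just after one weekly contact, is learned at the next, and that contact is treated as a visit: 7 + 7 = 14 days from onset. On the same clock a listed event takes 7 + 1 = 8 days.
3. The event starts just after a visit, the site learns of it at once, and entry waits for the next scheduled visit:
   - DEP: 21 + 7 = 28 days, or 21 + 3 + 7 = 31 with the visit late in its window.
   - RWP: 14 + 3 + 7 = 24 days.
   - OLE: 90 + 5 + 7 = 102 days.
   - Listed event: 1 day.

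Cases 2 and 3 rest on assumptions, because 10.1 ties its clock to a visit and states none for information received between visits. All these lags end at eCRF entry. The time until someone reviews the entry and adds it to the study-wide count is not stated and comes on top.

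**The case against.** The strongest reply is that the sponsor is not without information. Section 6.7 provides continuing review by the medical monitor and the DMC, and all AEs go on the eCRF. In the DEP, the intolerance text in 3.2 treats a Grade 3 AE as a general sign of intolerance, places de-escalation after discussion with the medical monitor, and requires discussion of a dosing gap of 3 days or more. Sites have weekly contact in the DEP and RWP. The affected class is narrow: earlier dose-limiting events were GI (1.7), and 6.2 lets medical judgment make an important event serious. The charter may say who counts.

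Much of this stands, and it rules out several stronger readings:
- A reader might infer that the rule could be met with no route to anyone able to act. The documents do not support that; the routes exist, and the defect is delay.
- A reader might take 28 or 102 days as what the plan prescribes. Those figures need a site to hold a known event until the next visit, which 10.1 does not instruct. In the OLE, where Table 6 lists no weekly contact, many events may first be learned at the visit, and case 1 (7 days) then applies.
- A reader might infer that a late halt lets dose escalation continue in enrolled participants. Under 3.4 the halt stops enrolment only; those already enrolled continue dosing until DMC review.

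The reply does not close the gap:
- Review depends on the event having been reported, and the scheduled DMC meetings in 6.7 follow participant milestones.
- Section 3.5 asks for contact before IMP is stopped only where feasible.
- Skipping 1 to 2 days needs no approval from the monitor, and RWP doses cannot be modified, so no de-escalation contact arises there.
- The sentences in 3.2 on de-escalation conflict. One makes discussion with the monitor a condition; a later one requires consultation when the reason is something other than a Grade 3 or higher or Grade 2 GI event, or for a second de-escalation. They must be reconciled before that contact can be relied on as notification.

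**Conclusion.** The mismatch is in the current text. Criterion 1 covers more events than the 24-hour duty, and a related Grade 3 or higher AE that is neither an SAE nor an AESI counts toward the halt with no expedited route. Followed as written, the protocol can delay recognition that the criterion is met.

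The best-supported size is about 7 days against 1 from site awareness at a visit. The figure of about 14 days assumes that a weekly contact counts as a visit. The figures of about 28 to 31 days (DEP) and 102 days (OLE) are upper bounds that assume entry waits for the next visit.

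The point is confined to criterion 1; criterion 2 and related death are already inside the 24-hour route. That the protocol does not name who keeps the count is a smaller matter, since the DMC charter may do so. How often such events will occur cannot be judged from the documents. This is an inexpensive improvement to a safety rule; it does not show that the rule or its threshold is wrong.

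**What to change.** In Protocol 6.4, add to the events reportable within 24 hours: any AE of Grade 3 or higher that the investigator assesses as related to SYNB1934v1, whether or not it is serious or an AESI.

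In Protocol 3.4, state who tracks the study-wide count against criterion 1, or cross-refer to the DMC charter if that is settled there.

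The stopping threshold stays as it is, and no visit or procedure is added. The cost is one sentence in each section and a few more expedited forms for sites.

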### 3.5. Study Discontinuation for Individual Participants

Reasons for discontinuation of IMP may include the following:

- The participant withdraws consent.
- The investigator or sponsor notes a significant noncompliance with protocol procedures (e.g., use of a prohibited concomitant medication).
- The participant develops an intolerable toxicity including but not limited to a Grade 3 or more severe AE or SAE assessed as related to IMP by the investigator.
- The investigator determines that the participant must discontinue further study dosing for medical reasons (including pregnancy).
- The participant has low levels of Phe ( $< 30 \mu\text{mol/L}$ ) or Tyr ( $< 20 \mu\text{mol/L}$ ) or has profound elevations in Phe ( $> 1.5 \times$  the DEP baseline value during DEP and RWP and  $> 2200 \mu\text{M}$  during OLE).

If possible, the investigator will confer with the sponsor or medical monitor before discontinuing dosing. Participants who discontinue from IMP in RWP will be encouraged to remain on study

and complete assessments (particularly safety assessments) through the remainder of RWP. Participants who discontinue from DEP and OLE will be asked to have an early termination visit 30 days after the last dose of IMP (see Section 5.6).

Participants may withdraw their consent at any time for any reason without prejudice to their future medical care by the physician or at the institution. If a participant withdraws consent, the date and stated reason for consent withdrawal should be documented. Participant data collected up to the date of consent withdrawal will be included in the analyses.

### **3.6. Duration of Study Participation**

The maximum time of study participation for a participant is planned to be approximately 6 months for screening through RWP and up to 36 months for Part 3:

- Screening: up to 45 days
- Part 1 (DEP): up to 15 weeks
- Part 2 (RWP): 4 weeks
- Part 3 (OLE): up to 36 months

The clinical trial concludes with the final visit of the OLE (36 months). No additional arrangements are made for the care of subjects following the completion of the trial, as they will be returned to the standard of care for PKU.

## **4. STUDY POPULATION**

### **4.1. Number of Participants**

This study plans to enroll [REDACTED]. More participants may be enrolled to achieve [REDACTED] randomized in Part 2.

### **4.2. Selection of Participants**

This study will enroll male and female participants  $\geq 18$  years of age. Participants will be eligible for enrollment in this study regardless of race/ethnicity.

